Therapeutic plasma exchange followed by convalescent plasma transfusion in severe and critically ill COVID-19 patients: A single centre non-randomized controlled trial

trial registration number: NCT04973488

Date: 3 August, 2020

Study design, setting and population

A total of 38 Caucasian patients will be included in the present single center non-randomized controlled trial. All patients included in the study will be adults (>18 years) who present with acute respiratory failure and ARDS, and have positive reverse transcriptase-polymerase chain reaction (RT-PCR) test results for SARS-CoV-2 virus upon hospital admission. ARDS is defined as acute-onset hypoxemia (P/F ratio <300) with >50% bilateral pulmonary opacities on chest imaging within 24-48 h that are not fully explained by congestive heart failure and that require ICU treatment and monitoring. Exclusion criteria are represented by any of the following: Pregnancy, patients with suspected or confirmed pulmonary embolisms and patients with terminal disease, patients < 18 years of age. Patients enrolled in the study will be divided equally, non-randomized, into two groups as follows: A treatment group who will benefit of sequential TPE and CVP transfusion in addition to the standard treatment for COVID-19, and a control group who benefit of only standard treatment for COVID-19 (antiretrovirals, corticosteroids, anticoagulants and antibiotics if deemed necessary) according to hospital protocols. All patients will provide written informed consent immediately after admission into the ICU regarding all the procedures performed during hospitalization, including the treatment scheme applied in the present study and the use of the resulting data in scientific research publications, with the assurance that they will remain anonymous. In cases where obtaining informed consent from the patients will not be possible due to their critical medical condition, a legal representative will be informed and provide written consent. The trial was approved by the Ethics Committee of 'Pius Brinzeu' Emergency Clinical County Hospital Timisoara (approval no. 91/03.08.2020).

Study protocol

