The blood type of the patients will be determined immediately upon being admitted to the ICU. In the treatment group, a dual lumen, 14 French, dialysis catheter will be used for vascular access, by placing it in the femoral vein under echographic guidance. A single TPE session will be performed on the Infomed HF 440 machine (Infomed SA), with a plasma/blood separation ratio of 20%, using 40 ml/kg fresh frozen plasma as the substitute. The circuit will be anticoagulated with unfractionated heparin during the procedure. Upon completion of the TPE session, each patient from the treatment group will be transfused with 500 ml of ABO compatible CVP. Patients will be carefully monitored

during both the TPE session and the CVP transfusion, and also after the procedures, in order to treat emerging complications.

[figure not shown]

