Patients from the treatment and control groups will receive standard treatment for COVID-19 according to hospital protocols, consisting of corticosteroids, antiretrovirals, anticoagulants and antibiotics if deemed necessary. Patients from both groups will be anticoagulated with subcutaneous nadroparine (Fraxiparine; Aspen Pharma Trading) in therapeutic dosage, once every 12 h, adjusted according to bodyweight (≤ 70 kg: 3,800 Anti-Xa IU; >70 kg: 5,700 Anti-Xa IU). Patients from the treatment and control groups will receive corticosteroids in the form of 16 mg dexamethasone (Dexamethason; Krka) divided into 2 doses, daily. Antiretrovirals administered will be the ones in the hospital COVID-19 protocol lopinavir/ritonavir (Kaletra; Hetero Labs, Ltd.), 300 mg b.i.d. and remdesivir (Veklury; Gilead Sciences), 200 mg loading dose, then 100 mg o.d. for 5 days. Antimalarial drugs will also be used, in the form of hydroxychloroquine (Plaquenil; Sanofi-Aventis), 400 mg b.i.d. loading dose, then 200 mg b.i.d. Upon clinical (fever, chills, sweats or aspect/quantity of bronchial secretions) and paraclinical (leucocytosis, CRP or cultures) findings of infection, empiric antibiotics will be started, until de-escalation following culture results will be possible. Patients will be intensively monitored, and daily clinical and laboratory data will be collected during the ICU stay. Outcomes monitored will be survival at 30 days, oxygenation (P/F ratio) (normal ratio >300) and inflammatory markers [CRP (normal range 0-5 mg/l), LDH (normal range 135-225 U/l) and ferritin (normal range 30-400 μ g/l)] at the 7-day follow-up, as assessed using ASTRUP analyses and blood tests.

Statistical analysis plan

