Statistical data will be analysed using GraphPad Prism 8 (GraphPad Software, Inc.) and IBM SPSS Statistics 20 (IBM Corp.). The category variables will be characterized by value and percentage. Continuous variables will be presented as mean (\pm standard deviation) and median (interquartile range). Data distribution testing will be performed using the Shapiro-Wilk test. The numerical variables will be compared with the t-test for independent samples or the Mann-Whitney U test, depending on the type of distribution of the variables. The χ^2 test (or Fisher's exact test) will be used for the nominal variables. The Kaplan-Meyer method with the log-rank (Mantel-Cox) test will be applied to evaluate the primary endpoint. Cox regression will be utilized to determine hazard ratio of the treatment group. All statistical tests will be calculated with 2 tails and $P<0.05$ will be considered to indicate a statistically significant difference.

Local Ethics Committee Decision regarding Scientific Research in Human Subjects

SPITALUL CLINIC JUDEȚEAN DE URGENȚĂ „PIUS BRÎNZEU” TIMIȘOARA

• [name]
• Cod fiscal 4663448 • Telefon [name] • [contact]
• e-mail: [contact] • www.hosptm.ro

91/03.08.2020

DECIZIA COMISIEI LOCALE DE ETICA PENTRU CERCETARE STIINTIFICA A SPITALULUI CLINIC JUDETEAN DE URGENȚA TIMIȘOARA

Va comunicam avizarea din punct de vedere etic a studiului clinic cu titlul:

"Therapeutic plasma exchange succeeded by convalescent plasma transfusion in critically ill Covid -19 patients - a single center non- randomized controlled trial"

Departamentul in care se desfosoara: Compartiment ATI – Covid, Spitalul Clinic Judetean de Urgenta "Pius Brinzeu" Timisoara, Sectia ATI Covid, Spitalul Clinic Municipal Lugoj

Persoane responsabile pentru desfasurarea studiului clinic: Conducator de doctorat- [name]. [name], Laborator Clinic Central, doctorand- dr. [name], Clinica ATI - Spitalul Clinic Judetean de Urgenta "Pius Brinzeu" Timisoara.

Studiul se va realiza in baza consintamantului informat semnat de catre pacient/ reprezentant autorizat al pacientului la internarea in spital, consintamant care cuprinde si investigatiile imagistice care se efectueaza pe perioada internarii. Se va asigura anonimizarea totala a investigatiilor, pentru a nu permite sub nici o forma identificarea pacientilor.

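### No baseline-adjusted analysis is stated for day-7 P/F ratio, CRP, LDH and ferritin in non-randomised groups, so a starting gap can be reported as a treatment effect

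*Combined protocol and SAP*

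**What the plan says.** Allocation, under Study design, setting and population: "A total of 38 Caucasian patients will be included in the present single center non-randomized controlled trial", and "Patients enrolled in the study will be divided equally, non-randomized, into two groups". That is 38 / 2 = 19 per group. The text gives no allocation rule, matching or stratification. Entry severity is bounded on one side only: "ARDS is defined as acute-onset hypoxemia (P/F ratio <300", with no lower limit.

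Outcomes, under Study protocol: 30-day survival, then P/F ratio and the three inflammatory markers "at the 7-day follow-up, as assessed using ASTRUP analyses and blood tests". None of the four is defined as a change from a starting value. The same section plans that "daily clinical and laboratory data will be collected during the ICU stay", but does not list which tests are daily. Treatment is described as "A single TPE session will be performed on the Infomed HF 440 machine", followed by convalescent plasma. The text shown does not say how long after ICU admission this happens or what day 7 is counted from.

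Methods, under Statistical analysis plan: "The numerical variables will be compared with the t-test for independent samples or the Mann-Whitney U test", the choice depending on distribution. The "log-rank (Mantel-Cox) test will be applied to evaluate the primary endpoint", so the four day-7 measures appear to be secondary. The only model named is a Cox regression for the treatment hazard ratio, with no covariates listed.

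**The concern.** Without randomisation, nothing makes the groups' starting P/F, CRP, LDH or ferritin comparable, even on average. If one group starts sicker, part of that gap will still be present at day 7. A two-sample test on day-7 values cannot tell that residue from an effect of plasma exchange plus convalescent plasma.

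A baseline table would show an imbalance but would not correct for it. With no adjusted analysis prespecified, any adjustment would be chosen after the data were seen, and a reader could not tell whether a positive result would have survived a planned one. Four outcomes are exposed in this way.

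**Working it through.** **Inputs from the documents.** 19 per group; two-sided tests at 0.05; unadjusted t-test or Mann-Whitney test. The plan gives no effect size, SD or power for 38 patients, so it has no figure of its own to reproduce.

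**Assumptions.** r is the within-group correlation between baseline and day 7, and d is the baseline gap in SD. Neither is in the documents, so four pairs spanning mild to marked are used. All 38 patients are taken to have day-7 values.

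**Model.** Day 7 = r × baseline + c × group + noise, with unit SD within group and no treatment effect. The term c is any group difference that baseline does not explain.

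**Unadjusted t-test.** The expected day-7 difference is r × d + c. The noncentrality is (r × d + c) × √(19/2), with 36 df. For r = 0.5, d = 0.5, c = 0: the difference is 0.25 SD, the noncentrality is 0.25 × 3.082 = 0.771, and the rejection rate is 11.7%.

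**ANCOVA on baseline.** The expected adjusted difference is c. Rates come from 40,000 simulated trials per setting.

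**Change score.** The standardised shift is (c − (1 − r) × d) / √(2(1 − r)), with 36 df.

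Three cases:
- A: baseline is the only difference, c = 0.
- B: the groups would keep a constant gap, c = (1 − r) × d. The day-7 difference is then d itself.
- D: unmeasured confounding of 0.3 SD runs against the baseline gap, c = −0.3.

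False-positive rates:

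| Case | Method | (0.3, 0.25) | (0.5, 0.5) | (0.6, 0.5) | (0.7, 0.8) |
|---|---|---|---|---|---|
| A | t-test on day 7 | 5.6% | 11.7% | 14.7% | 39.0% |
| A | ANCOVA | 5.0% | 4.9% | 5.1% | 4.9% |
| A | change score | 7.3% | 11.7% | 10.3% | 15.3% |
| B | t-test on day 7 | 11.7% | 32.3% | 32.3% | 67.0% |
| B | ANCOVA | 8.2% | 13.2% | 11.1% | 15.1% |
| B | change score | 5% | 5% | 5% | 5% |
| D | t-test on day 7 | 10.4% | 5.3% | 5.0% | 12.2% |
| D | ANCOVA | 15.3% | 16.9% | 19.1% | 21.1% |
| D | change score | 22.6% | 37.8% | 38.9% | 55.2% |

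Mann-Whitney on day-7 values is close to the t-test: 5.2%, 10.8%, 13.8%, 36.1% in A and 10.8%, 30.0%, 29.4%, 64.0% in B.

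**Which input drives it.** Because r and d rise together in the table, here is case A with each varied alone. At d = 0.5 the t-test gives 7.4%, 11.7% and 18.3% for r = 0.3, 0.5 and 0.7. At r = 0.5 it gives 6.6%, 11.7%, 20.3% and 32.3% for d = 0.25, 0.5, 0.75 and 1.0.

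**Power for a true 0.8 SD effect.** The unadjusted reference with balanced groups is 67.0%. ANCOVA gives:

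| r | d = 0 | d = 0.5 | d = 0.8 | d = 1.0 |
|---|---|---|---|---|
| 0.3 | 69.9% | 67.0% | 62.9% | 59.9% |
| 0.5 | 78.0% | 75.2% | 71.5% | 68.7% |
| 0.7 | 91.0% | 89.3% | 86.4% | 83.6% |

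**The case against.** **The sizes are assumed.** This stands. The documents give no r, d or unmeasured bias, and the planned t-test's rate runs from 5.0% to 67.0% across the cases shown. At the mild end of case A (5.6%) the problem is negligible. Entry at P/F below 300 also narrows the baseline P/F range and may put that outcome nearer the low-r end. The rates show what can happen; they do not predict it.

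**Adjustment does not cure confounding.** This also stands. ANCOVA removes bias only from the measured baseline value. In case D it does worse than the planned test, because there two biases partly cancel when neither is adjusted for.

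**The plan says only numerical variables.** It does not name the day-7 outcomes or say whether levels or changes are tested, and a t-test on changes would fit the wording. A reader might infer that starting values are definitely left out. The documents support only that no use of them is stated. A change score would not settle the matter either: 7.3% to 15.3% in A and 22.6% to 55.2% in D.

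**The timing may be in a figure.** A reader might infer that baseline and day 0 are undefined in the plan. The text shown does not state them, but a figure in the Study protocol section is not available here and could. The absence is not established.

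**The primary endpoint.** A reader might take this point to mean that the survival result is free of the problem. The documents do not support that: the log-rank test and Cox model also list no covariates. That analysis is outside this point.

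**Conclusion.** The point holds in a limited form. For four apparently secondary outcomes in non-randomised groups, the plan states only an unadjusted comparison, and a starting gap can be reported as a treatment effect. With no treatment effect, the planned t-test's false-positive rate is 5.6% to 39.0% if baseline is the only difference (ANCOVA about 5%), and 11.7% to 67.0% if the groups would keep a constant gap (ANCOVA about 8% to 15%). With unmeasured confounding in the opposite direction the order reverses: 5% to 12% unadjusted against 15% to 21% for ANCOVA. All of this rests on assumed r and d, the model above and 19 evaluable patients per group.

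The conclusion is therefore not that the planned test must mislead, nor that adjustment makes the comparison unbiased. It is that an inexpensive analysis which deals with the one measurable source of bias should be prespecified. It should be changed, but it is not a flaw that by itself invalidates the trial.

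**What to change.** - Make the main analysis of each day-7 outcome an ANCOVA with group and the same variable's baseline value, with the log scale fixed in advance for CRP, LDH and ferritin. Report the adjusted difference (P/F) or ratio (markers) with a 95% confidence interval.
- Use as baseline the last value before plasma exchange in the treatment group and a value at a matching time after ICU admission in controls. Count day 7 from that point in both groups. If the figure not shown already fixes this timing, the analysis text should refer to it.
- Report change from baseline as a supportive sensitivity analysis and discuss any disagreement. Do not require both to reach P<0.05. For a 0.8 SD effect at r = 0.3, 0.5 and 0.7, that rule would have power of 49%, 64% and 86% with balanced groups, and about 21%, 38% and 71% with a 0.5 SD baseline gap in the direction of the effect.
- State that unmeasured confounding remains, and that adjustment does not address day-7 values missing through death or ICU discharge. Report the number analysed per group.

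**Cost.** Plan wording and a little more analysis in SPSS, which the plan already names. It must be confirmed that baseline LDH and ferritin are measured. Power can be slightly lower when r is low and imbalance is large: about 63% at r = 0.3 and d = 0.8 for a 0.8 SD effect, against the 67% unadjusted reference with balanced groups.

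### Day-7 P/F ratio, CRP, LDH and ferritin are compared without baseline values, by a test that a normality pre-test selects, between groups that were not randomized

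*Combined protocol and SAP*

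**What the plan says.** The Statistical analysis plan states "Data distribution testing will be performed using the Shapiro-Wilk test". Numerical variables are then "compared with the t-test for independent samples or the Mann-Whitney U test, depending on the type of distribution of the variables". It gives no threshold for the normality test. It does not say whether each group, the pooled data or the residuals are tested, or what happens when the two groups give different verdicts. "All statistical tests will be calculated with 2 tails", at the 0.05 level.

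The outcomes concerned are listed at the end of the Study protocol section: P/F ratio, CRP, LDH and ferritin "at the 7-day follow-up, as assessed using ASTRUP analyses and blood tests". The same section provides for daily collection of clinical and laboratory data during the ICU stay.

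On numbers and allocation, the design section says "A total of 38 Caucasian patients will be included in the present single center non-randomized controlled trial" and "Patients enrolled in the study will be divided equally, non-randomized, into two groups as follows", which gives 19 per group.

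For description, the plan reports both mean (SD) and median (IQR). For these four outcomes it names no between-group effect measure, confidence interval, transformation or baseline term. The hazard ratio from Cox regression belongs to survival, not to them.

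**The concern.** Two features of the plan combine.

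- **Data-dependent test.** The t-test addresses a difference in means and Mann-Whitney addresses rank ordering. With 19 values per group and moderate skew, chance largely decides which is reported. CRP, LDH and ferritin may be judged by different tests in the same trial, with no common estimate to set side by side.
- **No baseline value.** A marker that is higher in one group at ICU admission tends to be higher there at day 7, whatever the treatment does. Randomization would make such a difference a matter of chance, already allowed for in the P value. Here nothing ensures that, so a baseline difference carries into the day-7 comparison and can look like a treatment effect or hide one. Leaving baseline out also discards information that would sharpen the estimate.

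At stake is how the four day-7 outcomes can be interpreted.

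**Working it through.** **Inputs from the plan.** N = 38 divided equally, so n = 19 per group; two-sided 0.05; Shapiro-Wilk, then t-test or Mann-Whitney. No power, effect, SD or distribution is stated, so there is no planned figure to reproduce.

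**Assumptions.** Log-normal markers with log-SD 0.3 to 1.2, or normal data with mean/SD of 3 or 5. Baseline to day-7 correlation ρ of 0.3, 0.5 or 0.7. All 19 per group evaluable at day 7. Mann-Whitney used if Shapiro-Wilk gives P<0.05 in either group, otherwise the t-test. Results are Monte Carlo, with 2,500 to 10,000 trials per setting.

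**Step 1. How far the test depends on chance.**

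| Log-SD | Mann-Whitney chosen | Groups give opposite verdicts |
|---|---|---|
| 0.3 | 41% | 36% |
| 0.5 | 74% | 50% |
| 0.8 | 97% | 30% |
| 1.0 | 99% | 16% |

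With truly normal data Mann-Whitney is chosen in about 9–10% of trials. At log-SD 0.5, if the three markers were independent, the chance that they do not all get the same test is 1 − 0.744³ − 0.256³ = 1 − 0.412 − 0.017 = 57%.

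**Step 2. Cost of the pre-test alone.** Overall type I error under the rule is about 4–6%. Power at an assumed shift of 0.934 SD:

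| Data | Rule | Fixed log-scale t-test |
|---|---|---|
| Log-normal, log-SD 0.3 | 78.7% | 79.7% |
| Log-normal, log-SD 0.5 | 77.7% | 79.9% |
| Log-normal, log-SD 0.8 | 76.4% | 79.2% |
| Log-normal, log-SD 1.0 | 76.7% | 80.5% |
| Normal, mean/SD 3 | 80.4% | 72.4% |
| Normal, mean/SD 5 | 79.4% | 78.4% |

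The log scale alone gains 1 to 4 points on log-normal data and loses 1 to 8 on normal data.

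**Step 3. Ignoring baseline when the groups differ.** Let the groups differ by 0.5 SD at baseline, with no treatment effect. The expected day-7 difference is ρ × 0.5 SD, and in standard-error units λ = ρ × 0.5 × √(19/2) = ρ × 1.541. The rejection rate of an unadjusted test is about Φ(λ − 1.96) + Φ(−λ − 1.96):

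- ρ = 0.3: λ = 0.462, about 7%
- ρ = 0.5: λ = 0.771, about 12%
- ρ = 0.7: λ = 1.079, about 19%

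Simulation of the full rule agrees to within about a point, at about 6–18% over this range. The log-scale model with baseline stays at about 5%.

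**Step 4. Power with balanced groups, assumed effect 0.95 SD on the log scale.** Unadjusted: Φ(0.95 × √(19/2) − 1.96) = Φ(2.928 − 1.96) = 83% for a test on the correct scale; simulation gives about 79% under the rule. Adjustment reduces the residual SD to √(1 − ρ²), so the standardized effect becomes 0.95/√(1 − ρ²):

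| ρ | Standardized effect | Normal approximation | Simulated, adjusted |
|---|---|---|---|
| 0.3 | 0.996 | 87% | 82–84% |
| 0.5 | 1.097 | 92% | 89–91% |
| 0.7 | 1.330 | 98% | 97–98% |

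The simulated values are lower because the normal approximation ignores the estimated variance and the chance baseline difference.

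**The case against.** **Inferences that go too far.** From the pre-test a reader might infer that false positives are inflated. They are not, overall. A rate of 8.5% does appear at log-SD 0.5, but only within the t-test branch, which is about a quarter of trials there. A reader might also infer that the rule loses material power against any fixed log-scale analysis. The documents give no distribution for any marker, so that cannot be asserted: the difference is small if the markers are log-normal and reverses if they are roughly normal. The large gains in Step 4 come from adjusting for baseline, which is a separate change from removing the pre-test.

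**Points that stand.**
- The 0.05 threshold and the either-group rule used in the check are assumptions, and the selection rates depend on them. At log-SD 0.8 or more, the choice is nearly fixed anyway.
- Three inflammatory markers are unlikely to be independent, so the 57% is only illustrative.
- Nineteen evaluable patients per group at day 7 is optimistic for severe and critically ill patients whose daily data stop when they leave the ICU. Losses would lower every power figure.
- Adjustment has a price when the groups really differ. At correlation 0.5, simulated adjusted power falls from 90% with no imbalance to 87% at 0.5 SD and 81% at 1 SD.
- Reporting both mean and median gives a common description across markers. It does not supply a between-group estimate with an interval.

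**Conclusion.** The concern holds for the four day-7 continuous outcomes. Their test and effect measure are not fixed in advance, no estimate with a confidence interval is named, and baseline differences between non-randomized groups pass straight into the comparison. The pre-test is the lesser part, and the main harm is ignoring baseline: about 6–18% false rejections, against about 5% with adjustment, under an assumed 0.5 SD imbalance and correlations of 0.3–0.7. With no imbalance, the power forgone at an assumed 0.95 SD effect is roughly 3 to 19 points over the same correlations (82–84% to 97–98%, less 79%).

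The SD, correlation, imbalance, distribution and 19 evaluable patients per group are all assumed, because the documents state none of them. The documents also do not show that the groups will in fact differ at baseline; the point is that the analysis does nothing about it if they do. Nor does adjusting for one marker's baseline remove confounding by other patient characteristics. The primary survival analysis is untouched. This should be changed, but it does not undermine the trial's main comparison.

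**What to change.** In the Statistical analysis plan:

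1. Delete the Shapiro-Wilk selection step.
2. For CRP, LDH and ferritin, prespecify a linear model of log(day-7 value) on group and log(baseline value). Report the ratio of geometric means with its 95% CI.
3. For the P/F ratio, use the same model on the original scale. Report the adjusted mean difference with its 95% CI.
4. Define baseline at the same point in both groups, before the plasma exchange in the treatment group.
5. Keep Mann-Whitney as a stated sensitivity analysis.

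The cost is a few sentences. Linear regression runs in the named software, and the daily laboratory collection should already supply baseline values. The downsides are that marker effects become ratios rather than differences, that some precision is lost if the groups differ strongly at baseline, and that a log scale can cost power for a marker that turns out to be roughly normal. In that last case adjustment usually makes up the loss: at correlation 0.5 the adjusted log-scale model still had 81–88% power on normal data (shift 0.934 SD), against 79–80% under the rule.

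### The groups are not randomised, yet the planned survival analysis names no adjustment, so any prognostic imbalance passes into the log-rank P-value and the hazard ratio

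*Combined protocol and SAP*

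**What the plan says.** **Allocation** (Study design, setting and population). "Patients enrolled in the study will be divided equally, non-randomized, into two groups as follows": a treatment group and a control group, 38 patients in total and so 19 each. The available text gives no rule for who goes into which group. One figure and some pages were not available to this review, so a rule stated there cannot be excluded.

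**Case mix** (same section). Patients are adults with ARDS: "ARDS is defined as acute-onset hypoxemia (P/F ratio <300", with bilateral opacities "that are not fully explained by congestive heart failure and that require ICU treatment and monitoring". Pregnancy, pulmonary embolism (suspected or confirmed) and terminal disease are excluded. No upper age limit, severity stratum or matching factor is named.

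**Analysis** (Statistical analysis plan). "The Kaplan-Meyer method with the log-rank (Mantel-Cox) test will be applied to evaluate the primary endpoint". A separate sentence adds the Cox model: "Cox regression will be utilized to determine hazard ratio of the treatment group". The remaining tests are also simple two-group comparisons: "The numerical variables will be compared with the t-test for independent samples or the Mann-Whitney U test", with chi-squared or Fisher tests for nominal variables. Everything is two-sided at 0.05.

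The plan does not name the primary endpoint. Survival at 30 days is the inference, because it is listed first among the outcomes (Study protocol) and is the only one that suits a log-rank test.

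**The concern.** Nothing in the described design makes the two groups comparable, and nothing in the described analysis compensates. The entry criteria narrow prognosis, but patients can still differ widely: any adult age qualifies, and any P/F ratio below 300. If the treated patients happen to be healthier, the treatment looks beneficial when it is not. If they are sicker, it looks harmful or a real benefit is hidden. In both cases a P-value below 0.05 no longer carries a 5% false-positive risk.

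Calling the trial non-randomised in its title discloses the problem without reducing it. The baseline comparisons can display a difference but do not remove it from the survival result.

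**Working it through.** The plan gives no power, effect size, mortality or dropout figure, so there is no stated number to reproduce beyond 38 / 2 = 19 per arm and the two-sided 0.05 level. What follows is an illustration; mortality, imbalance and prognostic strength are assumptions.

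**Step 1: deaths.** At 30%, 50% and 70% 30-day mortality, 38 × 0.3 = 11.4, 38 × 0.5 = 19 and 38 × 0.7 = 26.6, or about 11, 19 and 27 deaths.

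**Step 2: bias in the hazard ratio (HR).** If the groups differ by *d* SD on a prognostic score and each SD multiplies the hazard by *H*, the log-HR is shifted by at most about *d* × ln *H*:

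- 0.3 × ln 1.5 = 0.122, HR 0.89
- 0.5 × ln 2 = 0.347, HR 0.71
- 0.8 × ln 2.5 = 0.733, HR 0.48

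Omitting the score from the model pulls these somewhat towards 1, as the simulated values below show.

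**Step 3: simulation of the planned analysis.** 8,000 trials per scenario, 19 per arm, true HR 1, exponential survival censored at day 30, treated group healthier. Results are for 30/50/70% mortality.

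| Imbalance, prognostic HR | Crude HR | Log-rank error |
|---|---|---|
| none | about 1 | 4.5 / 5.0 / 5.2% |
| 0.3 SD, 1.5 | 0.91 / 0.89 / 0.89 | 5.2 / 6.0 / 6.5% |
| 0.5 SD, 2 | 0.73 / 0.74 / 0.75 | 7.8 / 10.3 / 11.4% |
| 0.8 SD, 2.5 | 0.52 / 0.56 / 0.58 | 18.7 / 24.0 / 28.8% |

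A separately written simulation gave 5.4/6.2/6.2%, 8.4/10.7/11.8% and 18.1/24.5/29.7% for the three imbalanced rows. With the treated group sicker, the crude HR is 1.34-1.38 at 0.5 SD and 1.72-1.90 at 0.8 SD.

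**Step 4: check by hand.** The standard error of the log-HR is about 2/√deaths. With 19 deaths it is 2/√19 = 0.459. At 0.5 SD, |ln 0.74| = 0.301 and 0.301/0.459 = 0.656. The error is Φ(−1.96 + 0.656) + Φ(−1.96 − 0.656) = 0.096 + 0.004 = 10.0%, against 10.3% simulated. At 0.8 SD, |ln 0.56| = 0.580, the shift is 1.264 and the error 24.4%, against 24.0%.

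**Step 5: a different model.** With one binary severity factor and 50% control mortality (10,000 trials per scenario), severe disease in 40% of treated and 60% of control patients with severity HR 2 gives 5.8% error. At 30% against 70% with severity HR 4 it is 17.5%. Over the scenarios tried, stratifying by severity gives 5.0-5.6%. That is a best case, because the stratifier is the whole confounder, measured without error.

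**Step 6: what adjustment achieves.** Firth-penalised Cox model, two covariates, penalised likelihood-ratio test before and after adjustment, 30/50/70% mortality:

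- Each covariate correlated 0.6 with prognosis, 0.5 SD: HR 0.75-0.76 becomes 0.87; error 7.4/9.7/11.0% becomes 5.8/7.0/8.1%. Bias removed: 1 − ln 0.87/ln 0.75 = 1 − 0.139/0.288 = 52%.
- Same, 0.8 SD: HR 0.55-0.58 becomes 0.74; error 17.7/23.2/28.1% becomes 7.7/10.2/12.4%. Bias removed at HR 0.57: 1 − 0.301/0.562 = 46%.
- Correlation 0.3, 0.8 SD: HR 0.60-0.62; error 14.3/18.8/22.9%. Bias removed at 50% mortality: 1 − ln 0.61/ln 0.57 = 12%. At 0.5 SD and 70% mortality, 0.76 to 0.77 is only about 5%. About 10% overall is a fair summary.
- Mild imbalance (0.3 SD), correlation 0.6: error 5.5/5.9/6.5% adjusted against 5.3/5.8/6.5% for the log-rank test, so unchanged, although the HR moves from about 0.89 to 0.95.

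**Step 7: baseline tests as a safeguard.** With 19 per arm, a t-test has 32% power to flag a true 0.5 SD difference and 67% for 0.8 SD.

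**The case against.** **The Cox sentence does not say the model is univariable.** True; covariates are not ruled out. But none is pre-specified, and the log-rank test that carries the primary endpoint is unadjusted in any case.

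**The magnitudes are assumed.** This stands. The documents give no mortality and no evidence that prognosis drove allocation. Large inflation needs 0.5-0.8 SD of imbalance; in the mild case the planned test is close to nominal. An assignment rule, if one exists, would bear on size and direction.

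**A reader might infer that the Cox hazard ratio is the primary result, or that open covariate choice inflates the primary test.** The plan supports neither. It assigns the primary endpoint to Kaplan-Meier and log-rank and never calls the hazard ratio primary. A two-group log-rank test has no covariates to choose. In simulation without imbalance, reporting the smallest Wald P among 16 candidate Cox models gives 9-14% error, against 4-6% for one fixed two-covariate model. That would concern only a Cox model whose covariates are chosen afterwards, and nothing in the documents suggests such selective reporting. It adds no weight to this point.

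**Adjustment may achieve little.** This partly stands. A correlation of 0.6 may be optimistic for age and P/F ratio, the latter being restricted by the entry limit. The benefit is real only if the covariates are prognostic and the groups differ appreciably.

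**Conclusion.** The point holds as an omission in the primary analysis. A non-randomised comparison is tested and estimated without any pre-specified adjustment, so prognostic imbalance in either direction passes into the log-rank P-value and the hazard ratio. Under the assumptions above, the false-positive rate lies between close to nominal and about 30%.

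A reader might go further and conclude that the result will favour the treatment, or that the error is inflated by a known amount. The documents do not support that: they give neither an assignment rule nor any baseline data, so size and direction in this trial are unknown. The omission itself is plain from the text and should be corrected before outcomes are analysed, because an adjustment chosen later carries less weight.

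**What to change.** Pre-specify, as the main treatment comparison, a Cox model with treatment, age and P/F ratio. Take both covariates at ICU admission in both groups, enter them as continuous and do not select them by significance. Report the log-rank test and crude hazard ratio as unadjusted supportive results. Show baseline balance as standardised differences, and word the conclusion as an association adjusted for measured confounders only.

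With about 11-27 deaths, no more than about two covariates can be supported. A Firth penalty with a penalised likelihood-ratio test is a reasonable option at these counts, but not essential.

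**Cost.** A few sentences of text. Age and P/F ratio are needed to apply the entry criteria, consent is sought on ICU admission ("All patients will provide written informed consent immediately after admission into the ICU"), and "daily clinical and laboratory data will be collected during the ICU stay", so no new measurement is required.

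**Downsides.**

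- The treatment standard error rises by about 5-8%.
- About half the bias remains with good covariates and about nine-tenths with weak ones; under mild imbalance the error rate is essentially unchanged.
- The Firth likelihood-ratio test runs at about 6-7% at 70% mortality with no imbalance, and may need other software.
- Adjustment does not remove any immortal-time bias that would arise if treated patients must survive from ICU admission to plasma exchange. The available text does not define the start of follow-up.
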